Inclusion criteria: (1) Aberrant Behavior Checklist-Community (ABC-C) ^{31,98} Irritability subscale score ≥ 8 ; (2) Leiter-II¹⁰⁶ Nonverbal IQ standard score ≥ 40 ; (3), meeting the Symptom Criterion score (minimum number of symptoms necessary for a DSM-V²⁷ mood, anxiety, or ADHD diagnosis) on the Child & Adolescent Symptom Inventory 5 (CASI-5);¹⁰⁷ and (4) a confirmed diagnosis of ASD by meeting clinical cut-offs on the Social Communication Questionnaire (SCQ)¹⁰⁸ (≥ 11)¹⁰⁹ and Autism Diagnostic Observation Schedule-2 (ADOS-2).¹¹⁰ Only one child with ASD per family will be included in the study to maintain independent observation of participants. Participants will also require a consistent caregiver (i.e., parent or legal guardian) to complete study outcome measures. We will not exclude participants taking medications, as this is a common occurrence for the target population. However, information regarding medications, dosages, and any changes during the study will be collected from caregivers. Medications or substances that could affect cardiovascular or electrodermal activity (e.g., amphetamines, anxiolytics, anticholinergics, beta blockers) or cortisol levels.¹¹¹ (i.e., smoking or regularly use oral, inhaled, or topical steroids), will be flagged and participant's physiological data collected may be excluded or controlled for in the analyses.

Exclusion criteria: Potential participants will be excluded for any of the following reasons: (1) medical or behavioral issues (e.g., animal abuse or phobia to horses) that prevent participation; (2) being a ward of the state; (3) is judged during the riding center screening to have significant riding experience, as the THR manualized curriculum¹⁶ is designed for beginner riders; (4) exceeding weight limits determined by the individual riding center sites' (Colorado and Maine) safety policies (5) vision, hearing, or physical impairments that would prevent participants from being able to be accurately evaluated (e.g. needing to see materials, see others, respond to questions) by study diagnostic measures or (6) unable to engage safely and independently with horses and others at the riding center. Of note, participants will not be allowed to begin baseline assessments until at least six months have passed from the time they last engaged in mounted EAAT, given pilot evidence for the six-month maintenance of THR effects.¹¹²

Study Design and Research Methods

(See Appendix for Calendar of Events/Timetable Document)

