Setting: To address Aims 1 and 2, all THR and BA control interventions and physiological data collection will take place at two Premiere accredited PATH¹⁷ international therapeutic riding centers: (1) Colorado: Hearts and Horses in Loveland and (2) Maine: Riding to the Top Therapeutic Riding Center in Windham. Note: study consent/assent and initial screening visits will occur at the following sites: Children's Hospital Colorado main campus and satellite clinic site locations, Colorado State University, and Maine Behavioral Healthcare/Center for Autism and Developmental Disorders clinic (CADD). The Colorado site is a large facility that has previously participated in our replication pilot¹⁸ and is located in a rural area that draws referrals from northern Colorado and southern Wyoming where intervention resources are limited for youth with ASD who require extensive services to address psychiatric issues and related aberrant behaviors. The Colorado site will also recruit participants for the waitlist/hybrid groups to address exploratory Aim 3a & 3b. The Maine site is located in close proximity to a large inpatient and outpatient psychiatric treatment center for youth with ASD in Portland (Maine Behavioral Healthcare/Spring Harbor Hospital). Therefore, the Maine site will also recruit ASD youth psychiatrically hospitalized at Spring Harbor Hospital to address exploratory Aim 3c. Please note Maine site is closed as of December 31, 2023.

Recruitment: IRB-approved study recruitment materials will be used for participant recruitment in communities (i.e., schools, ASD parent-support networks, and service agencies) near each of the two therapeutic riding centers. The Maine Site will recruit participants discharged from Maine Health's Spring Harbor Hospital's inpatient and partial psychiatric unit. At the Colorado site, participants will also be recruited via the COMIRB-approved study flier sent through Children's Hospital Colorado MyChart EPIC messaging system.

Pre-screening: Pre-screening will take place via REDCap survey or phone interview. Pre-screen questions are the same regardless of modality. Pre-screen questions are specific to study inclusion and exclusion criteria previously described. Those meeting initial pre-screening inclusion criteria will be scheduled for an initial screening visit at their respective locations (Children's Hospital Colorado or Spring Harbor Hospital, ME).

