Re-screening: Participants previously screened, consented and randomized, who have chosen to wait 6 months or longer to begin the intervention phase, will be re-screened with the ABC-irritability scale to ensure they still score ≥ 8 on that scale before they begin the intervention. Those not meeting ≥ 8 on the ABC-C -irritability scale will be excluded from the study.

Initial Screening (Visit I): As part of the informed consent/assent process, participants and their caregivers will be informed that they will receive modest monetary compensation for the pre-and post- speech therapy visits and for the six-month follow-up assessment visit (if randomized to the THR or BA group). They will also be informed that they will receive free 10-week interventions (THR, BA, or Hybrid). **The BA group will receive one free THR lesson following their completion of post-intervention assessments.** The youth's tolerance of study equipment (helmet, Shimmer3 EDA and ECG monitors with electrodes, and salivary cortisol collection swabs) follow successful procedures used in our pilot studies (e.g., social stories, modeling, desensitization). Participants will receive instruction on saliva-stimulating exercises using images and simulated chewing, as needed. Caregivers will be asked to complete the psychiatric diagnostic forms. Non-verbal IQ and ASD diagnostic screening assessments will be administered to youth to establish eligibility. If the youth meets screening criteria, the caregiver identified will be given the demographic forms to complete. The caregiver will be asked to identify a designated/consistent caregiver to complete pre-, during, post-and 6-mos assessment forms for reporter consistency. Participants meeting screening criteria will be randomized to study groups according to the randomization plan in the following section. Those participants will be given a riding center orientation packet to complete and return directly to the riding center prior to being scheduled for their riding center site screening visit (Visit II).

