Randomization: For the Colorado site, the study statistician will generate random group assignment numbers stratified according to Leiter-II¹⁰⁶ nonverbal IQ standard score (>85 NVIQ and ≤ 85 NVIQ) to assign treatment (THR) or control groups (BA or waitlist/hybrid). After at least 24 participants have completed the waitlist/hybrid arm, this assignment will discontinue. Those assigned to the waitlist group will, after completing their 10-week waiting period and post assessments, participate in the Hybrid group (5 weeks BA and 5 weeks THR). For the Maine site, the study statistician will generate random group assignment numbers as specified above to assign to the treatment (THR) or control group (BA).

Riding center site screening (Visit II): THR and BA participants will complete a 45-minute -individual screening at their study site's riding center with a THR instructor. In the event that a THR or BA participant could not complete this riding center for behavioral reasons (e.g., feeling overwhelmed by the novel environment), participants will be allowed no more than two attempts for this screening. This will involve interviewing caregivers about participants' needs and abilities, caregivers completing the ABC-C Irritability screener, as well as engaging participants in a review of riding center safety rules, and practice with physiological equipment (i.e., putting saliva sampling rod in mouth and wearing the Shimmer3 EDA and ECG monitors) . **For THR participants:** Sit at an art table and engage in an art or puzzle activity about horses, enter the arena, engage in a 10-minute mounted activity on the horse, and then dismount. **For BA participants:** Sit at art table and engage in an art or puzzle activity about horses. Participants will then be assigned to a THR or BA group appropriate to their age and abilities. THR participants will be matched with a horse based on their unique needs consistent with standard practices of the THR industry.¹⁷ Participants may be excluded from the study at this time due to exclusion criteria discussed earlier. The waitlist/Hybrid participants recruited for the Colorado site will follow both a combined version of BA and THR screening routine similar to the screening protocol previously described .

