Time 0 (T0) Baseline intervention assessments (Visit III): Within one month before week 1 of the intervention phase, all participants (THR, BA, Waitlist, Hybrid) will be individually scheduled to complete the SALT¹²⁷ with the speech therapist at their study site (Colorado or Maine). The speech assessment will be audiotaped and transcribed to allow scoring of this measure. Video and audio files will be stored on a secure, password protected drive on the Colorado and Maine Health sites secure network servers. On the first day of the 10-week intervention (THR, BA, or Hybrid) or wait period, caregivers will complete the ABC-C,⁹⁸ SRS™-2,¹²⁶ EDI,¹²⁸ the WHOQOL-BREF⁹⁵ , and the Crisis Mental Health Care Usage Survey

If caregivers decide to postpone their child's 10-week intervention after they have already completed baseline intervention assessments (Visit III) and their child has completed only up to two intervention lessons, caregivers will be asked to complete an additional baseline assessment (caregiver forms only). The initial completed baseline assessments will not be used for data analyses. Additionally, when the participant is ready to complete their 10-week intervention, they will not attend the one or two lessons they may have previously attended so that they will only complete up to 10 intervention lessons as part of their participation in the study.

Riding center site 10-week intervention (Visits IV-XIII): (See Appendix for an overview of THR and BA interventions).

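### Randomised children can be excluded before any baseline caregiver form is completed, partly through a visit that differs by arm, so the promised all-randomised analysis cannot be met for them

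*Protocol*

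**What the plan says.** **Allocation.** Under Initial Screening (Visit I), "Participants meeting screening criteria will be randomized to study groups according to the randomization plan in the following section". Only then are those children scheduled for Visit II.

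**Visit II.** Under Riding center site screening (Visit II), "Participants may be excluded from the study at this time due to exclusion criteria discussed earlier". The caregiver interview, ABC-C irritability screener, safety rules, equipment practice, art table and limit of two attempts are common to THR and BA. THR children additionally "enter the arena, engage in a 10-minute mounted activity on the horse, and then dismount". BA children do not.

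**Criteria settled at the centre.** The exclusion criteria cover a child who "is judged during the riding center screening to have significant riding experience" and one who is "unable to engage safely and independently with horses and others at the riding center".

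**Re-screening.** "Participants previously screened, consented and randomized, who have chosen to wait 6 months or longer to begin the intervention phase, will be re-screened" on ABC-C irritability, and those below 8 are excluded from the study.

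**Baseline forms.** Under Time 0 (T0), "On the first day of the 10-week intervention (THR, BA, or Hybrid) or wait period, caregivers will complete the ABC-C" and the other caregiver measures.

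**Analysis.** General consideration of statistical analysis promises that every randomised participant enters the ITT analyses. The mixed model is the main way of handling missing values, and the Aim 1 model uses baseline and end of treatment.

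**Drop rule.** Participant Discontinuation Criteria removes from the study any child who misses more than two of ten lessons.

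**The concern.** A child excluded at Visit II or at the re-screen has been randomised but has neither T0 nor T2 caregiver outcomes, and so contributes nothing on change to the mixed model. The ITT set then becomes, in effect, those who were randomised and survived the later checks.

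That would matter little if the checks worked identically in both arms without regard to allocation. At Visit II they do not fully do so. Riding experience and safe engagement with horses can be observed directly when a child is on a horse. In BA there is no mounted part, and BA lessons involve no horse contact. If removals differ by arm, the analysed arms are no longer the randomised arms.

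The drop rule is a separate and weaker point. It ends participation for the non-adherent children whom the ITT rationale says the analysis should reflect, and the protocol provides no T2 or T3 forms for them.

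**Working it through.** **1. Order of events**

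| Step | Protocol section | Caregiver outcome data available |
|---|---|---|
| Randomisation | Initial Screening (Visit I); Randomization | Screening ABC-C irritability only |
| Possible exclusion | Riding center site screening (Visit II) | Irritability screener repeated, no T0 set |
| Possible exclusion after a wait of six months or longer | Re-screening | Irritability scale, no T0 set for analysis |
| T0 caregiver forms | Time 0 (T0), first day of intervention or wait | First full set |
| Possible drop for missed lessons | Participant Discontinuation Criteria | T0 and weekly ABC-C up to the drop |
| T2 and T3 forms | Time 2 and Time 3 | Not provided for after exclusion or drop |

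Children removed in the second or third row have no T0 or T2 set, so the all-randomised promise fails for them. Children removed in the fifth row have T0 data and can enter the mixed model under missing-at-random. For them ITT is weakened but not impossible.

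**2. The plan's own power figures**

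Two-sample t test, d = 0.62, two-sided 5% (the protocol does not state sidedness):

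- 81 per arm (Table 2): 97.5%, against the stated 97%.
- 71 per arm (text): 95.6%.
- 56 per arm (completers): 90.2%, against the stated 90%.

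The figures reproduce to within 2 points, and the concern does not depend on them. If 5% to 20% of 71 per arm were lost before T0 in both arms, n would be 67.5 to 56.8 and power 94.7% to 90.6%. The loss of power is modest. Selection is the main issue.

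**3. Illustration of bias**

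The overall mean of an arm is (1 − f) × retained mean + f × excluded mean. Hence retained mean − overall mean = f × (retained − excluded). With the same gap in both arms, the between-arm bias is (net difference in f) × gap. Neither f nor the gap is in the protocol, so both are assumptions.

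SD of change, from Power analysis:

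- From the SEMs: 1.66 × √27 = 8.63 and 1.8 × √26 = 9.18, pooled 8.90.
- From the stated d: (6.9 − 2.3)/0.62 = 4.6/0.62 = 7.42.

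SE in SD units is √(2/n): 0.168 at n = 71 and 0.189 at n = 56. Type I error = P(|Z + bias/SE| > 1.96).

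| Net f | Gap (SD) | Bias (SD) | Bias (points) | Share of 4.6 | Type I, n = 71 | Type I, n = 56 |
|---|---|---|---|---|---|---|
| 0 | any | 0 | 0 | 0% | 5.0% | 5.0% |
| 5% | 0.5 | 0.025 | 0.19–0.22 | 4–5% | 5.25% | 5.20% |
| 10% (about 7 of 71) | 0.5 | 0.05 | 0.37–0.45 | 8–10% | 6.02% | 5.81% |

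**The case against.** - **Arm difference.** No sentence says the mounted activity decides eligibility. It stands next to group assignment and horse matching, which may be its purpose. The exclusion criteria apply to both arms, most of Visit II is shared, and before allocation "Pre-screen questions are specific to study inclusion and exclusion criteria previously described". This stands as a limit: differential exclusion is a possibility, not something shown. It does not remove the problem, because the protocol itself leaves the judgement of riding experience to the riding centre, after allocation.
- **Baseline value.** An irritability score is on file from screening and from Visit II, and an SAP could name it as baseline. A T0 speech sample may also precede removal. Both are true. But the other caregiver measures have no such score, and without T2 the child adds nothing on change.
- **Postponers.** Some children complete T0 and up to two lessons before postponing. Their first forms exist, but the protocol says they will not be analysed.
- **Re-screen.** It is worded alike for all arms and re-applies an inclusion criterion. No bias is demonstrated there. It still removes randomised children, and does so on the primary outcome scale.
- **Size.** The illustrated bias is small and rests on assumed inputs. That limits the severity but does not resolve the contradiction.

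**Conclusion.** The concern holds and should be fixed. The sections on Visit I, Visit II and re-screening cannot be reconciled with the all-randomised ITT statement for children removed before T0. That conclusion rests on the stated order of events and on no numerical assumption. Choosing an analysis set in an SAP would not cure it, because the outcomes would not exist.

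The size and direction of any bias cannot be determined from the protocol. Under assumed net exclusion differences of 5% and 10% with a 0.5 SD gap, the bias is 0.025 and 0.05 SD against a planned 0.62, with type I error about 5.2% to 6.0%. It is zero if similar children are excluded equally in both arms. The drop rule is secondary: it leaves ITT possible but makes the T2 and T3 results lean on missing-at-random more than they need to.

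**What to change.** 1. Reconcile the Visit II, re-screening and discontinuation sections with the ITT statement by separating leaving the lessons from leaving the study. Unless consent is withdrawn, caregiver forms continue: T0 at removal if not yet done, T2 ten weeks after T0, and T3 six months after T2 for THR and BA. The child stays in the ITT set in the allocated arm. T0 at removal falls at a different point from the usual first-day baseline, so its timing should be recorded and reported.
2. Report exclusions after randomisation by arm and reason.
3. Optionally, where enrolment is still open and it is practical, complete the arm-neutral checks (caregiver interview including riding experience, weight limit, any re-screen) before the allocation is released. The mounted activity would still follow allocation, so this reduces the problem without removing it.

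The rules on who may attend lessons are not questioned here. Items 1 and 2 cost a wording amendment and questionnaires from a few families. Item 3 costs earlier staff time and possibly travel for each Colorado candidate. It cannot help at Maine, which closed on December 31, 2023.

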Salivary Cortisol: Cortisol can be measured accurately in a minimally invasive manner via saliva, and the hypothalamic Pituitary Adrenal (HPA) axis is fast acting in response to environmental conditions. Typically, HPA activity shows a distinct non-linear circadian rhythm. In TD individuals, cortisol levels increase before awakening, show a rapid rise from awakening to +30-45 min, and a daily fall, with levels lowest during the normal sleep cycle before repeating.¹¹⁹ Circadian cortisol rhythms in children with ASD are not always consistent with matched TD controls, instead displaying lower AM and higher PM levels.¹²⁰ However, preliminary evidence suggests that afternoon salivary cortisol levels in ASD youth are less irregular, indicating that afternoon sampling may be a more reliable measure of stress for this population.¹²¹ Each participant will donate approximately 0.5-1 mL of saliva at the riding center immediately before and 20 minutes after each THR or BA group session weeks 1-10. Salivary cortisol collections will only be analyzed for weeks 1, week 5 or the adjacent week if participant misses session 5, and week 10. Collection methods will be the same as previously reported in our replication pilot.¹²² In brief, THR and BA interventions will occur in the afternoons (between 1:00-5:00 PM) to avoid the sharp rise and fall in cortisol levels in the AM associated with diurnal patterns of HPA axis activity. Only saliva samples taken at weeks 1, 5, and 10 of the intervention will be assayed for cortisol. Saliva samples will be collected using absorbent swabs designed for use with youth (Salivabio, LLC, Carlsbad, CA). They will be temporarily stored frozen at the riding centers, then transported to the respective hospital research site for storage in a freezer until shipped to Salimetrics for analysis. Caregivers will receive the following instructions prior to collection days: (1) Participants should avoid eating a substantial meal (other than a snack) and drinking liquids other than water within 30 minutes prior to collection time and (2) cannot brush their teeth for at least 45 minutes prior to collection time. Participants who do eat within the hour before collection will be asked to drink water and then wait 10 minutes before collections.¹¹¹

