Heart Rate (HR) and Heart Rate Variability (HRV): The Shimmer3 cardiac (ECG) monitor has also been successfully used in studies involving youth with ASD similar to our target population, and is the frontline instrument used in the lab of our physiology expert co-investigators to measure participants' HR and HRV. The Shimmer3 ECG monitor weighs 28 grams (dimensions 3 x 1 ½ x ½ inches). This cardiovascular monitor was specifically developed to record electrocardiographic signals while participants are active or in motion. The form factor is compact (about 2" by 1"), lightweight (13g), and designed to wear continuously and unobtrusively. It samples ECG and HRV up to 2,048 Hz, which is sufficient for research.¹²⁵ It has a built-in accelerometer for quantifying periods of physical activity, necessary to identify

signal artifacts in post-processing. Although the Shimmer3 ECG assessments will be taken weekly during the 10-week intervention, these assessment data points will only be analyzed for weeks 1, week 5 or the adjacent week if participant misses session 5, and week 10.

Physiological Data Interval Recording Log: During weeks 1-10 of the THR and BA interventions, study personnel will record the start and end times using a stopwatch synchronized to system clocks in the Shimmer3 EDA and ECG monitors for each of the following activity periods: 3 to 5-minute baseline (art table activity); 45-minute THR (mounted) or BA lesson; 15-minute THR (grooming) or BA (scrapbook) closure activity; 20-minutes post (art table activity). These records will enable precise segmentation of cardiovascular and electrodermal activity data, enabling cross-condition analyses within-session and across-session change over time.

Physiological Sample Collection Log: During weeks 1-10 of the THR and BA interventions, caregivers will complete a log to report information that may affect physiological measurements, including participant's sleep the night prior to the lesson,^{41,42} particular stressors that occurred that day, and medications or physical health status changes.

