Participants (THR, BA, Hybrid in Colorado only) will attend intervention sessions at the riding center in their recruitment state (Colorado or Maine). THR and BA control group times will be between 1:00-5:00 PM in order to collect salivary cortisol when levels typically decline.¹¹¹ Hybrid group times will also occur within this same afternoon time period for consistency, even though salivary cortisol samples will not be collected. Intervention groups (THR, BA, Hybrid) will consist of 2-4 participants, be led by a THR instructor, follow a consistent routine, and learn horsemanship skills via activities tailored to ASD learning styles outlined in the THR manual.¹¹⁶ Each week of the intervention phase (THR, BA or Hybrid), caregivers will complete the ABC-C,⁹⁸ rating their child's behaviors over the past week prior to the current lesson. THR Intervention: Each participant will have an assigned horse and volunteer(s) (one horse leader and up to two side walkers). Similar to the RCT¹¹³, every effort will be made to enable each participant to ride a consistent horse throughout the study. Barn Activity Intervention: Each participant will have one assigned volunteer and will have no contact with horses at the riding center, just view horses at a distance. There will be a life-sized stuffed horse in the BA group for hands-on learning related to the weekly topic.

For THR and BA participants only: To increase compliance with mediator assessments, each week prior to starting the groups, participants will follow a consistent routine of wearing both their Shimmer3 EDA and ECG devices. The Shimmer EDA device will be worn on the wrist of participant's non-dominant hand and the Shimmer3 ECG cardiac monitor will be adhered to the chest wall area using adhesive electrodes. Participants will sit at a group art table with their respective small group (THR or BA) while study personnel will instruct participants to place the 10cm long foam swab rod under their tongue for one minute while watching a 1-minute timer. THR participants will then don their riding helmets and enter the riding arena and the BA will begin their group activity at the group table. Each week after conclusion of the THR and BA interventions, participants will sit with their respective groups (THR or BA) at an art table for 5 minutes followed by another saliva sample.

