Time 1 (T1) Mediator assessments taken weekly during the 10-week intervention, but will only be analyzed for weeks 1, midpoint, and 10. Physiological data (HR, HRV, and EDA) measurements will be taken continuously during the entire intervention lessons. Sections of analysis will be segmented from: (a) Three to five-minute seated art activity baseline before either intervention; (b) 45-minute THR riding or BA activity; (c) 15-minute THR grooming and tacking or BA scrapbook activity; and (d) 5-minutes post intervention that includes a seated art activity. RAs will annotate time and relevant activity levels for each period to correspond to device timestamps. Salivary cortisol samples will be taken during the five-minute seated baseline before THR or BA intervention and again 5 minutes post intervention. Caregivers will complete the Physiological Sample Collection Log each week of the 10-week intervention.

Time 2 (T2) Post- intervention assessments (Visit XIV): On the last day of the 10-week intervention (THR, BA, Hybrid) or waitlist period, caregivers will complete the ABC-C,⁹⁸ SRS™-2,¹²⁶ EDI,¹²⁸ , the WHOQOL-BREF⁹⁵ , and the Crisis Mental Health Care Usage Survey. Within one month of the conclusion of week 10 of the intervention phase, all participants (THR, BA, waitlist, and Hybrid) will be individually scheduled to complete the SALT¹²⁷ with the same speech therapist they saw for the Pre-intervention SALT at the Colorado or Maine hospital site. If there is a speech therapist personnel change from a participant's pre- to post- intervention SALT assessment visit, this change will be noted in the REDCap database to control for personal novelty bias in the analysis.

Time 3 (T3) Six-month post-intervention assessment (Visit XV): Only THR and BA participants will be individually scheduled to complete SALT¹²⁷ with the speech therapist at their study site (Colorado or Maine). During this visit, caregivers will complete the ABC-C,⁹⁸ SRS™-2,¹²⁶ EDI,¹²⁸ , the WHOQOL-BREF⁹⁵ , and the Crisis Mental Health Care Usage Survey. If there is a speech therapist personnel change from a participant's post- to 6-month post- intervention SALT assessment visit, this change will be noted in the REDCap database to control for personnel novelty bias in the analysis.

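### As written, the one-minute pre-session saliva swab falls inside the 3–5 minute seated baseline used for HR, HRV and EDA, and no rule removes that minute

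*Protocol*

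**What the plan says.** Four places in the Protocol bear on the timing.

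- **Time 1 (T1) Mediator assessments** defines the physiological segments. The first is "a) Three to five-minute seated art activity baseline before either intervention" and the last is "d) 5-minutes post intervention that includes a seated art activity". The same paragraph adds: "Salivary cortisol samples will be taken during the five-minute seated baseline before THR or BA intervention and again 5 minutes post intervention".
- **Riding center site 10-week intervention (Visits IV–XIII)** describes the routine. With both monitors already on, children sit at the art table and are told to "place the 10cm long foam swab rod under their tongue for one minute while watching a 1-minute timer"; the lesson then begins. Afterwards they sit "at an art table for 5 minutes followed by another saliva sample". Both arms do this every week.
- **Physiological Data Interval Recording Log** has staff time four whole periods by stopwatch, the last being "20-minutes post (art table activity". The swab is not one of the timed events. The stated purpose covers comparisons within a session as well as across sessions.
- **Salivary Cortisol**, under Study Measures, has saliva collected "immediately before and 20 minutes after each THR or BA group session weeks 1-10".

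The cleaning rules in **Data auditing and cleaning** deal with lost data, ectopic beats, movement and signal artefact. They do not mention the swab.

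**The concern.** The pre-session segment is meant to show the child at rest with a quiet activity. As written it also contains a study procedure: a foam rod held in the mouth while the child watches a timer. A child sitting still with a swab in place would pass a movement filter and a signal-quality check, so the minute would stay in the data. On the T1 and Visits IV–XIII timing, the post-session segment holds no such minute, so the two seated segments do not measure the same condition.

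This matters because the Background expects riding itself to raise arousal and looks for calming in the seated periods before and after it. If the swab raises HR or EDA, a fall from pre to post would look like calming in either arm. H1c is worded as change within the THR group from baseline to week 10. If the reaction fades over the weeks, the pre-session value would drift in the direction that H1c predicts.

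**Working it through.** There is no figure in the plan to reproduce. The check sets the timing statements side by side and then asks how far one minute can move a segment mean.

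**Step 1. Timing statements**

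| Protocol section | Before the session | After the session |
|---|---|---|
| T1 | segment (a) 3–5 min; sample within a five-minute seated baseline | segment (d) 5 min; sample at 5 min |
| Visits IV–XIII | one-minute swab at the art table, then the lesson | 5 min at the table, then the sample |
| Interval Recording Log | 3–5 min art table | 20 min art table |
| Salivary Cortisol | sample just before the session | sample 20 min after |

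Before the session the statements fit together and place the swab in the baseline. After it they conflict. On the first two rows the swab comes after segment (d). With the log's 20-minute period and T1's sample at 5 minutes, it falls inside the post period. With the sample at 20 minutes, it falls at the end of a 20-minute period.

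**Step 2. Share of the segment.** One minute out of L minutes is 1/L: 1/3 = 33%, 1/4 = 25%, 1/5 = 20%.

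**Step 3. Shift in mean HR.** For a rise of r bpm confined to the swab minute, shift = r/L. The documents give no r, so these values are assumptions.

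| Assumed r | L = 3 | L = 4 | L = 5 |
|---|---|---|---|
| 2 bpm | 0.67 | 0.50 | 0.40 |
| 5 bpm | 1.67 | 1.25 | 1.00 |
| 10 bpm | 3.33 | 2.50 | 2.00 |

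**Step 4. Skin-conductance responses per minute.** If the rate in the swab minute is k times resting (assumption), the segment rate is (k + L − 1)/L times resting.

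- k = 1.5: 3.5/3 = 1.17 and 5.5/5 = 1.10
- k = 2: 4/3 = 1.33 and 6/5 = 1.20
- k = 3: 5/3 = 1.67 and 7/5 = 1.40

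The segment rate is thus too high by 10–17%, 20–33% or 40–67%. HRV indices are not simple means over time, so neither formula gives their shift.

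**Step 5. Pre–post artefact (post minus pre), r = 5 bpm**

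- Post segment of 5 min without the swab: 0 − 5/3 = −1.67 to 0 − 5/5 = −1.00 bpm.
- Post segment of 20 min containing the swab: 5/20 − 5/3 = −1.42 to 5/20 − 5/5 = −0.75 bpm.

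The mismatch shrinks on the second timing but does not vanish.

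**Step 6. Week 1 to week 10 within one arm, r = 5 bpm.** If a fraction h of the reaction is lost, the artefact is −h·r/L.

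- h = 0, same window: 0.
- h = 0.5: −0.83 (L = 3) to −0.50 (L = 5) bpm.
- h = 1: −1.67 to −1.00 bpm.
- h = 0, but the window changes between 5 and 3 min: ±(5/3 − 5/5) = ±0.67 bpm.

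**Step 7. Between arms.** With equal r and L, the artefact in the arm-by-time interaction is −(h_THR − h_BA)·r/L, which is 0 when habituation is equal. It also stays 0 only if reaction size and window length match between arms.

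**The case against.** The strongest case against is that the planned tests are largely protected. H1a–1c are assigned to the arm-by-time interaction, and path a regresses the mediator change on arm. Both arms follow the same swab routine, so a common reaction cancels. It also cancels across weeks, because the swab is taken in every week's baseline. This stands. A reader might infer that week-to-week change necessarily contains the swab reaction, or that the THR–BA contrast is biased. The documents support neither. Across weeks only habituation or a varying window remains. A constant offset adds no variance to change scores either; noise would need child-to-child differences in habituation or window, for which no figure is available.

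Second, a reader might take the post-session segment to be free of the swab. That holds on the T1 and Visits IV–XIII timing but not on every combination with the log and cortisol descriptions.

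Third, the screening visit might be read as evidence that the swab is poorly tolerated, since equipment tolerance is to "follow successful procedures used in our pilot studies (e.g., social stories, modeling, desensitization". That sentence covers helmet, monitors and swabs together, and the simulated chewing belongs to saliva production. The preparation, repeated with the sampling rod at the riding center screening, if anything reduces habituation after week 1.

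Fourth, T1 speaks of a 3–5 minute segment but a five-minute baseline for the sample, and the swab comes just before the lesson. A shorter art segment could end before it. This is possible but not stated, so inclusion is likely rather than certain.

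Fifth, trimming a segment is often left to an analysis plan or processing manual. That is fair for the cut, but less so for the order of procedures and the time stamp: without a logged swab time, the minute cannot later be removed exactly.

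**Conclusion.** The point holds with modest stakes. On the T1 and Visits IV–XIII text, a study procedure fills 20–33% of the pre-session physiological segment, and nothing removes it. Within-session pre–post differences, which the recording log is designed to allow, can contain a reaction to the swab. So can a within-THR reading of H1c, if children habituate or the 3–5 minute window varies.

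The size, and even the direction, of any reaction is an assumption: 2 to 10 bpm in that minute would move the segment mean by 0.4 to 3.3 bpm. The THR–BA time interaction and path a are unbiased provided reaction, habituation and window length are the same in both arms, and nothing in the documents indicates that they differ. The conflict over post-session timing is a separate textual defect. It also decides how unequal the two seated segments are.

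**What to change.** 1. In the Interval Recording Log, Visits IV–XIII and T1 text, record the undisturbed seated art activity first and take the swab after it. This matches the post-session order in Visits IV–XIII. It costs a sentence in each place and about one extra minute before the lesson.
2. If the order must stay, add the swab's start and end to the existing log and cut that interval from segment (a) for HR, HRV and EDA. The cost is one more logged event and one line in the segmentation rule. A 3-minute baseline would then keep only about 3 − 1 = 2 usable minutes, which is why the first option is preferable.
3. Fix one baseline window length for all children and weeks in place of a 3–5 minute range.
4. Reconcile the Salivary Cortisol, Interval Recording Log, Visits IV–XIII and T1 descriptions so that the post-session period has one length and the post-session sample one time.
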